## GUIDANCE ON TOXICITY MANAGEMENT FOR SPECIFIED TOXICITIES:

CONDITION AND SEVERITY	FOLLOW-UP AND MANAGEMENT
ELEVATIONS in ALT	
Grade 2 and higher – Oral Phase	
Oral phase: A Grade 2 ALT abnormality reported at Week 2 or Week 4, regardless of relatedness to the study product, should be confirmed within one week. Oral study drug may continue until the confirmatory results are available; no injections should be administered until confirmatory results are available during consideration of the Week 4 ALT value. If the repeat value is <math>\leq</math> Grade 2 at Week 3, study drug may continue to Week 4. If the repeat value is <math><</math> Grade 2 at Week 4, the participant may proceed to the injection phase. If the repeat value is Grade 2 or higher at Week 4, study product should be stopped, and the participant will be discontinued from the study. All such cases must be reported to the CMC. In addition, participants will be followed with weekly ALT assessments until they return to <math>\leq</math> Grade 1.

Grade 3 and higher – Oral Phase	
Oral Phase: A Grade 3 or higher ALT abnormality, regardless of relatedness to the study product, will result in permanent study product discontinuation and will prohibit a participant from entering the injection phase of the study. All such cases must be reported to the CMC. In addition, participants will be followed with weekly ALT assessments until they return to <math>\leq</math> Grade 1.

CONDITION AND SEVERITY	FOLLOW-UP AND MANAGEMENT
ELEVATIONS in ALT	
Grade 2 and higher – Injection Phase	
Injection phase: The CMC should be notified as soon as possible.
 
For a Grade 2 ALT, the CMC will determine whether further injections may be given in cases where levels are <math>\leq</math> Grade 2 prior to the next scheduled injection. Unless otherwise specified by the CMC, for Grade 2 ALT, repeat testing should be performed weekly until levels are <math>\leq</math> Grade 1.

Grade 3 and higher – Injection Phase	
Injection Phase: For Grade 3 and higher ALT, study product will be permanently discontinued. For Grade 3 and 4 ALT, repeat testing should be performed as soon as possible, and participants should be followed weekly until levels are <math>\leq</math> Grade 1. Participants who are permanently discontinued from study product should continue to be followed 48 weeks post-last injection.

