**Table 5.1. Management of Participants with AEs in Step 1**

Grade of AE	Brief Instruction
Grade 1 AE	Proceed with SOE and to Step 2
Grade 2 AE, excluding ALT	Proceed with SOE and to Step 2
Grade 2 ALT	At Enrollment or Week 2 → continue oral product, repeat ALT labs in 1 week At Week 4 → continue oral CAB, repeat ALT labs in 1 week If result is $\leq$ Grade 1, participant may move to Step 2 if otherwise qualifies;

	If result is $\geq$ Grade 2, permanently discontinue oral CAB, do not move to Step 2 and repeat ALT weekly until $\leq$ Grade 1, then terminate from study
Grade 3 AE, excluding ALT & CPK	Report to CMC and if determined to be: 
 
Related AE <math>\rightarrow</math> permanently stop oral product, follow until stabilizes and then terminate from study
 
NOT related AE <math>\rightarrow</math> follow CMC guidance
 

Grade 3 ALT	Report to CMC  Permanently discontinue oral CAB, do not move to Step 2 and repeat ALT weekly until $\leq$ Grade 1, then terminate from study
Grade 3 CPK + $<$ Grade 3 ALT	Report to CMC for adjudication
Grade 4 AE, excluding ALT & CPK	Report to CMC  Permanently stop oral product, follow until stabilizes and then terminate from study
Grade 4 ALT	Report to CMC  Regardless of CPK permanently stop oral product, repeat ALT labs weekly until $\leq$ Grade 1, then terminate from study
Grade 4 CPK + $<$ Grade 3 ALT	Report to CMC for adjudication

#### 5.4 Transitioning from Step 1 to Step 2

Conditions in Step 1 that could disqualify a participant from transitioning to Step 2 are as follows:

- Pill count suggestive of less than 50% adherence at the Week 4 visit;
- Missed or delayed Week 4 visit;
- Specific AEs per Table 5.1;
- At substantial risk of HIV infection and/or qualifies for oral PrEP by local guidelines;
- Any HIV reactive/positive test (see SSP).

If any of the above conditions occur, investigators should notify the HPTN 083-01 CMC at [contact] within one week of awareness for final determination of fitness to enter Step 2.

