The ECLAIR study, conducted at 10 US sites, screened 205 individuals in order to enroll and randomize 127 HIV-uninfected low-risk men. Participants received daily oral CAB 30 mg or daily oral placebo in a randomized 5:1 ratio during the 4-week oral lead-in phase. One participant randomized to active study product (oral CAB and CAB LA) withdrew prior to the oral lead-in due to being incarcerated. During the oral lead-in, 11 participants withdrew prior to their first injection, all of whom were randomized to CAB LA, seven for AEs and four for other reasons. Ninety-four (94) participants received at least one injection of CAB LA 800 mg and 21 participants received at least one injection of placebo. Of those that started injections 95% (20 of 21) of those randomized to placebo and 93% (87 of 94) of those randomized to CAB LA completed all three injections. The participant in the placebo arm who did not complete all three injections reached a protocol-defined stopping criteria (he acquired HIV infection after his second injection). Four participants on the CAB LA arm withdrew after their second injection, citing injection tolerability as a primary reason. Three other participants discontinued study participation after receiving injections for non-AE and non-injection-related reasons.

Fifteen participants experienced a Grade 1 or higher ALT and 14 experienced a Grade 1 or higher AST. There were no Grade 3 or 4 ALT elevations. AE events leading to withdrawal included transient neutropenia (three participants), transiently elevated CPK (three participants), and fatigue (one participant). Two SAEs were reported, one deep vein thrombosis on placebo that was considered possibly drug-related and one appendicitis on CAB LA that was not considered drug related. Eighteen participants reported Grade 3 ISR pain.

Grade 4 treatment emergent CPK elevations with concomitant AST and/or ALT elevations were noted in four participants at the Week 4 visit, leading to early withdrawal in three participants. One of the four participants described a new rigorous exercise regimen prior to the Week 4 study visit; a second of these events resolved despite ongoing exposure to study product. All four Grade 4 abnormalities were resolving at one-week follow-up visits and have subsequently returned to normal off study product.

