## **12.0 APPENDICES I – XVI**

## 12.1 APPENDIX I. SCHEDULE OF EVALUATIONS – ORAL PHASE (STEP 1)

WEEKS in Study (Shaded column = dispense oral product)	Screening	WEEK 0 Enrollment	WEEK 2	WEEK 4
ADMINISTRATIVE, BEHAVIORAL, REGULATORY				
Informed consent	X			
Locator information	X	X	X	X
Demographic information 	X	X		
HIV prevention counseling	X	X	X	X
Offer condoms	X	X	X	X
Patient Health Questionnaire-9 (PHQ-9)		X		
Behavioral/Acceptability Assessment (CASI)		X		X
CLINICAL EVALUATIONS & PROCEDURES				
Dispense study product (enough for 5 weeks)		X		
Observe participant take oral study product 		X	X	X
Adherence counseling/pill count (pill count Weeks 2 and 4 only)		X	X	X
Medical history, con meds, targeted physical exam 	X	X	X	X
Hep B vaccination (if needed) 			X	
Blood collection	X	X	X	X
Urine collection	X	X		
Rectal swab collection	X			
LOCAL LABORATORY EVALUATIONS & PROCEDURES				
HIV testing 	X	X	X	X
HBV and HCV testing 	X	X		
CBC with differential	X	X	X	X
Chemistry testing 	X	X	X	X
Liver function tests 	X	X		X
Fasting lipid profile 		X		
Syphilis testing	X			
GC/CT testing (urine, rectal, and oral pharyngeal swabs)	X			
Urinalysis (protein and glucose; this test can be done at either the clinic or in the local laboratory)		X		
Plasma storage 	X	X	X	X

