### FOOTNOTES FOR APPENDIX I:

 Demographics may be collected and reported at either Screening or Enrollment.

 Staff are required to observe participants take one pill at Enrollment. If participants return with their pills at Weeks 2 & 4, staff will observe participant take one pill then as well, unless the participant has already taken oral study product that day. Participants must not be asked to take a second dose of oral study product for the sake of observation.

 Full physical exam is to be conducted during Enrollment. A targeted physical exam will be done at all other visits. Participant pulse, blood pressure and weight must be recorded at every visit. BMI must be calculated.

 The initial dose of the Hep B vaccination will ideally be given at Week 2, though there is flexibility around the timing of the vaccination. Subsequent doses may be given at different visits than indicated in this SOE, as long as sites follow manufacturer guideline timing.

 The HIV testing algorithm is provided in the SSP Manual. Testing for acute HIV must be negative and must be performed within the 14 days prior to enrollment of the participant. If HIV rapid testing is indicated, this testing may be performed in the clinic or the laboratory. At least one HIV assay result must be available and reviewed the same day as sample collection and before product is administered.

 Participants will be tested for Hepatitis B surface antibody (HBsAb), and Hepatitis B core antibody (HBcAb, total) at Screening or Enrollment. HbsAg and HCV Ab must be resulted and reviewed prior to enrollment.

 At Screening: Creatinine. At and after enrollment: BUN/urea, creatinine, CPK, calcium, phosphorous, glucose, amylase, and lipase.

 At Screening: ALT and TBili. At and after Enrollment: AST, ALT, total bilirubin, and alkaline phosphatase.

 Total cholesterol, HDL, triglycerides, and LDL (either calculated or measured). Participants must have fasted for at least 8 hours, preferably 12 hours, prior to sample collection. Do not collect or test if <8 hours fasting.

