6. TRIAL PARTICIPANT DISPOSITION

6.1 Disposition of Participants

The study will recruit participants to ensure that at least 50 participants progress to the injection phase, therefore more than 50 participants will be screened and enrolled.

Consort Diagram

¹Conditions in Step 1 that could disqualify a participant from transitioning to Step 2 are as follows:

- Pill count suggestive of less than 50% adherence at the Week 4 visit
- Missed or delayed Week 4 visit
- Grade 2 ALT at week 4, or grade 3 and above ALT anytime in step 1
- Grade 3 AE that is related to study product anytime in step 1, excluding ALT & CPK
- Grade 4 AE anytime in step 1, excluding ALT & CPK
- Grade 3 and above CPK and < Grade 3 ALT
- At substantial risk of HIV infection and/or qualifies for oral PrEP by local guidelines
- Any HIV reactive/positive test

Participant enrollment inclusion and exclusion criteria (see study protocol)

A. Inclusion Criteria

- 1) Assigned male at birth (including MSM, TGW, and gender non-conforming people)
- 2) At enrollment, below 18 years of age
- 3) At enrollment, body weight ≥ 35 kg (77 lbs.)
- 4) Willing to provide written informed assent/consent for the study and/or able to obtain written parental/guardian informed consent
- 5) Self-reported sexual activity with a male in the past 12 months
- 6) In general, good health, as evidenced by the following laboratory values:
 - a. Non-reactive / negative HIV test results
 - b. Absolute neutrophil count > 799 cells/mm³
 - c. Platelet count $\geq 100,000$ /mm³
 - d. Hemoglobin > 11 g/dL
 - e. Calculated creatinine clearance ≥ 60 mL/minute using the modified Schwartz equation (\leq grade 2)
 - f. Alanine aminotransferase (ALT) < 2.0 times the upper limit of normal (ULN) and total bilirubin (Tbili) $\leq 2.5 \times$ ULN
 - g. Hepatitis B virus (HBV) surface antigen (HBsAg) negative and accepts vaccination
 - h. HCV Antibody negative
- 7) Willing to undergo all required study procedures
- 8) If currently on PrEP from a non-study source, willing to stop said PrEP prior to enrollment and agree to switch to oral CAB for the lead-in period and CAB LA injections.

B. Exclusion Criteria

- 1) Co-enrollment in any other HIV interventional research study or other concurrent studies which may interfere with this study (as provided by self-report or other available documentation);
- 2) Past or current participation in HIV vaccine trial with exception for participants who can provide documentation of receipt of placebo;

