6.4 Unplanned enrollment discontinuation

In January 2022 the HPTN leadership determined that the study accrual rate was insufficient to meet the target enrollment in a reasonable amount of time, and study enrollments were stopped after a total accrual of nine participants.

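### The oral-phase ALT rules act on a Week 2 result, but the Step 1 schedule draws no liver function test at Week 2

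*Protocol*

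**What the plan says.** Two places set actions for a Grade 2 ALT found at Week 2. Protocol Table 5.1 covers a result "At Enrollment or Week 2": oral product continues and ALT is repeated in one week. Protocol Appendix VI (oral phase) covers "A Grade 2 ALT abnormality reported at Week 2 or Week 4", asks for confirmation within a week, and says what to do with a Week 3 repeat.

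The stopping rule is stricter and names no week. Appendix VI states: "A Grade 3 or higher ALT abnormality, regardless of relatedness to the study product, will result in permanent study product discontinuation". Table 5.1 has the same rule, and SAP Section 6.1 lists among the conditions that can keep a participant out of Step 2: "Grade 2 ALT at week 4, or grade 3 and above ALT anytime in step 1".

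The schedule is in Protocol Appendix I. Its row for "Liver function tests" is marked at Screening, Week 0 and Week 4 and is blank at Week 2. Blood collection, HIV testing, CBC, chemistry and plasma storage are all marked at Week 2. Footnote 7 gives the chemistry panel: "At and after enrollment: BUN/urea, creatinine, CPK, calcium, phosphorous, glucose, amylase, and lipase". ALT appears only in the liver panel (footnote 8). Protocol Section 5.3 refers to Appendix I for the Week 2 laboratory work and orders no separate ALT.

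**The concern.** The safety rules and the schedule that should feed them do not match. Section 1.10 justifies the lead-in as the means of finding acute toxicity, through repeated safety assessments, before a depot that cannot be removed. Section 5.3 calls Week 2 a safety visit, and Appendix II tests liver function at every Step 2 visit, including visits a week apart. Nothing in the text read for this point explains why Week 2 should be the exception.

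What is at stake is how early oral drug is stopped in an adolescent with a Grade 3 or higher ALT rise. It is not who receives the injection.

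Three other provisions are affected to a lesser degree:

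- CPK is drawn at Week 2, but the Grade 3 and Grade 4 CPK rows of Table 5.1 apply only when ALT is below Grade 3. Without a Week 2 ALT, a site cannot tell whether the CPK row or the ALT stopping row governs. Section 6.3 reports four ECLAIR participants with Grade 4 CPK and concomitant AST and/or ALT elevations at Week 4.
- Expedited reporting under Section 6.2.2 needs ALT together with total bilirubin, and both come only from the liver panel.
- SAP Section 12.2 counts Grade 2 or higher laboratory abnormalities in the oral phase. An ALT rise that appears and resolves before Week 4 would not be counted.

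**Working it through.** The plan gives no figure to reproduce. The check sets the schedule against the rules and then does simple day and dose arithmetic.

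**Schedule against rules, Step 1**

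| Visit | Liver panel (Appendix I) | Chemistry, no ALT | Rule that needs an ALT |
|---|---|---|---|
| Screening | marked | marked | eligibility |
| Week 0 | marked | marked | Table 5.1, Grade 2 |
| Week 2 | blank | marked | Table 5.1 and Appendix VI, Grade 2; Grade 3+ stop |
| Week 4 | marked | marked | Table 5.1 and Appendix VI, Grade 2; Grade 3+ stop |

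The blank does not look like a table-reading fault. The row keeps an empty third cell and a mark in the fourth, in line with the rows around it.

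**Delay**

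- First scheduled on-treatment ALT as written: 4 × 7 = day 28.
- First on-treatment ALT implied by the Grade 2 rules: 2 × 7 = day 14.
- Extra time on drug for a Grade 3+ rise already present at day 14: 28 − 14 = 14 days.
- Extra drug: 14 × 30 mg = 420 mg.

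Laboratory turnaround comes on top of either draw date, so the difference stays at 14 days if turnaround is the same for both. Section 1.10 allows for it at Week 4: the fifth week of oral dosing covers the wait for those results.

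**How often it might matter**

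The only relevant count used here is from ECLAIR (Protocol Section 6.3): "There were no Grade 3 or 4 ALT elevations".

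- Adults who started oral CAB: 94 who were injected + 11 who withdrew in the lead-in = 105. As a check, 105 + 21 on placebo + 1 who withdrew before the lead-in = 127, the number randomized.
- One-sided 95% upper bound for 0 of 105: 1 − 0.05^(1/105) = 0.028, or 2.8%.
- Planned enrollment: 50 + 7 = 57, the upper end of the allowance in SAP Section 2.5. Expected count at the bound: 0.0281 × 57 = 1.6.
- Actual enrollment: nine (SAP Section 6.4). Expected count at the bound: 0.0281 × 9 = 0.25.

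These are expected counts at an upper confidence limit, not maxima. The ECLAIR statement is not limited to the lead-in. A Grade 3+ rise that is present at Week 2 and silent is a subset of what the bound covers, so the bound is conservative for this purpose.

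**The case against.** The strongest reply is that the rules naming Week 2 are Grade 2 rules, and under both of them product continues. The rule that stops drug names no week and acts on any ALT that becomes available. This is right. It means the 14-day comparison rests on the Week 2 draw that the Grade 2 rules presuppose, not on a date in the stopping rule. It does not supply the missing test.

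Other routes to an ALT exist. Enrollment ALT is scheduled, and a Grade 2 value there is repeated in one week. Week 2 includes a history and targeted examination, Appendix VI requires product to be held or discontinued when there are signs of clinical hepatitis, and Section 5.15 allows interim visits. These narrow the gap to a participant without symptoms whose Enrollment ALT was unremarkable. For that participant nothing is scheduled before day 28.

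It can also be said that the neighbouring schedules have mismatches of their own. In Appendix II, rectal swabs are collected at Week 34 but rectal testing is marked at Week 33. In Appendix III, blood tests are marked at early discontinuation with no blood collection. That is a reason to check the cell against the signed protocol, but it does not explain away a row whose marks line up with its neighbours.

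Finally, deleting the Week 2 and Week 3 wording would also make the documents agree. It would leave the 28-day gap in place and sit badly with the purpose given in Section 1.10.

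**Conclusion.** The concern holds. As written, the Week 2 branch of the ALT rules has no routine test to trigger it, and the Grade 3+ stopping rule cannot act on scheduled data before about day 28. The cost is up to about 14 further daily doses (420 mg) for a participant with a silent Grade 3+ rise at Week 2.

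The likely number affected is small: an expected count of no more than about 1.6 of 57 planned, or 0.25 of nine enrolled, at the 95% bound. This assumes that adolescents resemble the ECLAIR adults. The Week 4 ALT gate before the first injection is intact, and the primary safety window in SAP Section 8.1 starts at the first injection, so the primary analysis is not affected.

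Two sources were not available for this point: Protocol Section 1.8 on hepatic events and the SSP Manual. The manual may order a Week 2 ALT in practice, but that would not remove the conflict within the protocol.

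**What to change.** In Protocol Appendix I, mark liver function tests (at least ALT) at Week 2. Footnote 8 already defines the panel for all visits from Enrollment on, so it needs no change. The full panel is preferable to ALT alone, because total bilirubin is needed for the expedited-reporting criterion. The first scheduled on-treatment ALT then moves from day 28 to day 14, and the CPK rows of Table 5.1 can be applied at Week 2.

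The cost is one added panel per participant, from blood already collected at that visit: 57 panels at the planned size. Because "study enrollments were stopped after a total accrual of nine participants" in January 2022, the change corrects the plan and would serve any later protocol built on it. For this trial, the report of oral-phase laboratory abnormalities under SAP Section 12.2 should say that no ALT was scheduled between Week 0 and Week 4.

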## GUIDANCE ON TOXICITY MANAGEMENT FOR SPECIFIED TOXICITIES:

### Creatinine Clearance

CONDITION AND SEVERITY	IMMEDIATE ACTION	FOLLOW-UP AND MANAGEMENT
CREATININE CLEARANCE		
Estimated CrCl< 60 mL/min	Discontinue study product temporarily	If the calculated creatinine clearance is <60mL/min, it should be confirmed within 1 week of the receipt of the results, and the CMC should be consulted.
Confirmed CrCl< 60 mL/min	Permanently discontinue study product	If the calculated creatinine clearance is confirmed to be <60 mL/min, the CMC must be notified and the study product must be discontinued. Participants who fail to have a confirmed test within 2 weeks of receiving the initial result, should be discontinued from use of the study product until CMC adjudication and recommendation for further testing and follow-up.
Re-testing result is ≥60 mL/min	Consult CMC for guidance	If re-testing yields a result ≥ 60 mL/min, the IoR must consult the CMC for further guidance on resuming study product use, continuing the hold temporarily, or progressing to permanent discontinuation.  If the IoR, in consultation with the CMC, has determined that the case has stabilized, it may be possible to decrease the frequency of follow-up laboratory testing in addition to resumption of study product.

## GUIDANCE ON TOXICITY MANAGEMENT FOR SPECIFIED TOXICITIES:

### Creatine Phosphokinase (CPK)

#### Note the following for cases of exercise-induced CPK abnormalities:

Note the following for cases of exercise-induced CPK abnormalities: Cases of CPK abnormality  $\geq$  Grade 3 or higher, presumed to be exercise induced, accompanied by < Grade 3 ALT must be brought to the attention of the CMC for adjudication of further management and further administration of study product. Grades 3 and 4 elevations in ALT, regardless of CK elevation will prompt permanent discontinuation of study product and the participant will be followed for 48 weeks post-last injection. All such cases must be reported to the CMC.

CONDITION AND SEVERITY	IMMEDIATE ACTION	FOLLOW-UP AND MANAGEMENT
Creatine Phosphokinase		
Grade 3	Continue study product until repeat test results are available	A Grade 3 or higher elevation in CPK should result in a repeat assessment within 2-4 weeks to ensure the result is transient or due to exercise and will not require a change in study treatment. A history regarding use of products known to cause increase of CPK (such as statins), physical activity, or exercise preceding the CPK evaluation should be obtained.
Grade 4	Continue study product until repeat test results are available if the elevation is thought to be possibly or probably related to study product.	Grade 4 elevations in CPK should have a repeat assessment after the subject has abstained from exercise for >24 hours. For persistent Grade 4 CPK elevations that are considered possibly or probably related to the study product, study product should be discontinued and the participant should be followed on study/off study product.

